Social workers and family support workers in eligible teams are eligible to receive Kitbags. Family support workers who work in the eligible statutory teams are eligible to be part of our

sample as they do a considerable amount of the direct work with the children and young people. We consider team managers as not eligible because they are unlikely to do much direct work with children and young people. Social workers and family support workers who have permanent contracts are given the Kitbags to keep, and so if they leave the local authority's employment, a new Kitbag will need to be given to their replacement. (Agency workers leave at a sufficiently high rate that they will be asked to leave the Kitbag with their team for their replacement if they leave). We also allow for 15% contingency to account for these circumstances. If social workers or family support workers change teams within the local authority, they are asked to adopt the treatment assignment of their new team to prevent contamination but for analysis purposes they will be considered according to their original team treatment allocation.

Foster carers and kinship carers

Additionally, local authority foster carers and kinship carers who care for children supported by social workers and family support workers in treated teams will receive a Kitbag. Foster carers who care for children supported by social workers and family support workers in treated teams and employed by independent fostering agencies or other local authorities are not eligible to receive a Kitbag. This is to concentrate the resources with the participating local authorities. By kinship carers, we mean carers of children who are looked after on a voluntary, interim or full care order whose placement type is a placement with a relative or friend. The children supported by social workers and family support workers in treated teams will still have the opportunity to benefit from the Kitbag through their social worker or family support worker.

Local authorities may recruit new foster carers and kinship carers may start their caring responsibilities over the intervention period, and these foster carers and kinship carers who are caring for children supported by a social worker in a treated team will be given a Kitbag. We also allow for 15% contingency to account for these circumstances.

Table 2: Number of Kitbags for each local authority

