Carers (including kinship and foster carers) will be identified and recruited through the same mechanisms as social workers/family support workers. The birth parents of children in care will not be included as participants.

English as an additional language

In order to complete their working responsibilities, we assume that social workers and most foster carers have a level of English language comprehension that would allow them to fully participate in the evaluation if they wish to. Where this is not the case (e.g. EAL is a bit more common for foster carers who foster unaccompanied asylum seekers), we shall ask social workers if they can support the foster carer to answer the questions.

Randomisation

Randomisation will take place at the level of the team in a two-armed clustered trial, stratified by local authority and the team type (CIN / CP; CLA; children with disabilities). We will

⁶ Department for Education (2019) Characteristics of children in need tables: 2019, Table B4. <https://www.gov.uk/government/statistics/characteristics-of-children-in-need-2018-to-2019>

randomise at the social worker team level for three reasons. Firstly, the randomisation is not at the level of the child or young person because the resource is not given to the child or young person but used in direct work with the child and family by the social worker, family support worker, or foster carer. Secondly, the randomisation is not at the social worker level because social workers in the same team would be expected to discuss practice and there would be a risk of contamination. Thirdly, an element of the intervention is the use of Kitbag by social workers and family support workers in their team setting, for example in team meetings. While contamination may still be possible cross-team (or even cross-organisation), we believe that this is sufficiently limited that team-level randomisation remains most appropriate, when considering trade-offs with statistical power.

Each social worker or family support worker gets their own Kitbag if they are in one of the treated teams. Each in-house foster carer or kinship carer who is caring for a child or young person supported by a social worker or family support worker in a treated team will receive a Kitbag.

We will stratify at the local authority/team type level to ensure balance on the level of children's social care involvement that the teams focus on⁷.

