If the sample is imbalanced with respect to team type (CIN / CP, CLA, children with disabilities) within the local authority, we will re-randomise (setting a new seed). We take imbalance to be the proportion of teams of that type within the local authority assigned to the intervention to be greater than 0.75 or less than 0.25 (i.e. $\frac{3}{4}$ or $\frac{1}{4}$ teams) except where there is only one team of that type in the local authority.

We will also report the mean proportion of social workers to family support workers, and the mean proportion of permanent staff to agency staff, by treatment allocation but will not re-randomise if there is imbalance in treatment allocation on these variables. With a relatively small number of teams to allocate, we have decided to prioritise team type (within the local authority) to enable us to compare the impact of the programme on these subgroups.

Data collection

We have several data collection methods:

Impact evaluation

- Children and young people:
 - administrative data to measure children's social care involvement
- Social workers:
 - online survey to measure self-efficacy, stress
 - administrative data to measure sickness absence
- Foster/kinship carers:
 - online survey to measure self-efficacy

⁷ Due to a delay of the required data from Oxfordshire County Council, the randomisation was conducted for the three other local authorities first, and the teams from Oxfordshire County Council were allocated separately.

Sample size / MDES calculations

		MDES (Proportion of a Standard Deviation)
MDES		0.127
Proportion of variance in child's outcome explained by:	Child covariates (including baseline measure)	0.8
	Social Worker team covariates	0.1 (3 covariates)
Intraclass correlations (ICCs)	Team	0.03
Alpha		0.05
Power		0.8
One-sided or two-sided?		Two-sided
Level of intervention clustering		Social worker team
Average cluster size		150 children in each team
Sample Size (children)	Intervention	4500
	Control	4500
	Total	9000
Sample Size (teams)	Intervention	30 (15 per local authority)
	Control	30 (15 per local authority)
	Total	60

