MDES was determined by the Excel macro PowerUp⁸ for a 3-level fixed effects blocked cluster random assignment design with treatment at level 2 (BCRA3_2f). The three levels are individual (as we're detecting power for the primary outcome this is the child / young person), social worker team and local authority with treatment assigned at the social worker team level to 50% of the teams. One would not expect high intraclass correlation within teams themselves

⁸ Dong, N. and Maynard, R. A. (2013). *PowerUp!*: A tool for calculating minimum detectable effect sizes and sample size requirements for experimental and quasi-experimental designs. *Journal of Research on Educational Effectiveness*, 6(1), 24-67. doi: 10.1080/19345747.2012.673143

as cases aren't assigned to a team on the basis of similarity other than the level of social work involvement (child in need, child protection etc) (0.03). Baseline is expected to be highly predictive of endline SDQ score (0.8).

Outcome measures

The aim of Kitbag is to improve children's emotional literacy and ability to understand, express and regulate their emotions as well as improving their behaviour and relationships with others. The primary outcome measure is emotional and behavioural difficulties. The other outcomes are secondary outcomes.

Primary Outcomes

Child Outcomes

1i) Children's social care involvement

Given that we may have concerns about selection bias into the primary data collection, we shall also estimate the impact of the Kitbag programme on administrative outcomes which can be collected for all children and young people in the eligible population. Although children's social care administrative outcomes are more tangentially related to Kitbag and are also more difficult to change in a relatively light touch intervention, they have the benefit of not being subject to attrition bias. Kitbag will be delivered to children and young people with all levels of social work involvement, and the logic model does not suggest that it will be particularly beneficial for children and young people with particular children's social care profiles. The third secondary outcome measure is the level of children's social care involvement (2iii). Specifically, this is operationalised as the sum of escalations and de-escalations over the course of the intervention (May 2021 - May 2022):

- case closed
- child on child in need plan
- child on child protection plan
- child in care

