- for social workers and family support workers: the social worker or family support worker was a member of a team assigned to the intervention at point of randomisation and 0 else;
- for foster / kinship carers: the carer cares for a child or young person whose case is held at the point the foster carer enters the sample, by a social worker who is a member of a team assigned to the intervention at point of randomisation and 0 otherwise.

Although there is some turnover of social workers, family support workers and foster carers, about 80% of those at T0 (April 2021) will still be working with the local authority at T13 (May 2022), and so 80% will have received the full 12 months of the intervention. Binarising the treatment seems a reasonable proxy in this case.

For the outcomes relating to children, treatment is coded as a binary variable. When children enter the sample, at either the point of randomisation, or the point they become eligible (e.g. their case opens and meets other criteria) they will be allocated to treatment if the team of their allocated social worker was randomised to treatment.

Covariates

Including control variables increases the precision of the estimate. In each regression, we control for a number of relevant covariates. We outline different categories of covariates below.

Site effects

We include site fixed effects but not site-treatment interaction terms.

Previous outcome measures

We control for the previous measurements of the outcome variable where data is available. For the survey-based measures for social workers, family support workers and foster carers, the same measures will be asked at T6 (October 2021) and T13 (May 2022), and for administrative data we expect previous values to be available. For the outcomes of the CYP and parents / carers (including kinship carers), the previous measure of the outcome will be at T0 (April 2021) or when they entered services if they entered services after T0 (April 2021).

Other covariates

For CYP outcomes (primary outcome i) and secondary outcome i)), we include the following vector of individual-level covariates:

- gender (coded as male, female, or other/missing)
- age group (4-11, 12-17, 18 years, or missing with 4-11 as the reference category)
- ethnicity (Asian / Asian British, Black / African / Caribbean / Black British, Mixed / Multiple ethnic groups, Other ethnic group, White, missing; with the majority group as the reference category)

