Children are clustered into sibling groups, households (e.g. with other children in foster care) and caseloads (i.e. a group of children have the same social worker) and social worker teams. Because of this clustering, observations within one group (sibling group, household etc) may be more similar with each other on various characteristics compared with observations in other groups violating the assumption of independence. When data is structured in this way, the estimation of the treatment effect remains unbiased but the standard errors may be misspecified, leading to problems with inference. To correct for this, standard errors will be clustered at the level of randomisation, the social worker team level, in line with WWCS statistical guidance. This also accounts for correlations between observations at lower levels of nesting.

Handling non-compliance

If CYP are transferred to another team (e.g. due to a change of status), it is possible that the team to which they are transferred was ineligible for participating in the programme or had a different intervention / comparator group allocation. If a social worker or family support worker changes teams, it is possible that their new team had a different intervention/ comparator allocation. For all our analysis, we will conduct intention to treat analysis where a CYP is considered as treated if they are / were supported by a social worker who is a member of an intervention team at the point they entered the sample (either at randomisation or when their case started), irrespective of their use of Kitbag.

Multiple Comparison Adjustments

We will adjust for multiple comparisons within the secondary outcomes using Hochberg's step-up procedure, as per WWCS statistical guidance.

Regression specification

For social workers, family support workers and foster carer outcomes:

$$Y_{ict13} = \beta_0 + \beta_1 D_c + \beta_{2:4} A_c' + \beta_5 Y_{ict0} + \beta_{6:k+6} X_i' + \beta_{k+6:k+11} M_c' + \epsilon_c$$

Where:

- Y_{ict13} is the dependent variable for individual i , team c at the end of the trial, $t13$. β_0 is the intercept
- D_c is the treatment variable
- A_c is a vector of the local authority fixed effects
- Y_{ict0} is the "pre" outcome of individual i in team c , at their "pre" data collection point, $t0$
- X_i' is an $N \times k$ matrix of characteristics of individual i
- M_c' is an $N \times 5$ matrix of characteristics of team c
- ϵ_c is the error term clustered at the team level c

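### Secondary outcome 5: a carer's chance of being coded treated rises with the number of randomised teams holding the carer's children, and the plan neither fixes an index team nor adjusts for this

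*Protocol*

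**What the plan says.** Under Analysis plan, Independent variable of interest: treatment, a carer is coded 1 if "the carer cares for a child or young person whose case is held at the point the foster carer enters the sample" and that case sits with an intervention team. Every other carer is coded 0. The exploratory models (Impact on CYP with different levels of CSC involvement, Impact on CYP by age, Contextual Factors Analysis) repeat the singular wording.

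Kitbags are supplied on the same basis. Participants, Foster carers and kinship carers, states that "local authority foster carers and kinship carers who care for children supported by social workers and family support workers in treated teams will receive" one, and the Randomisation section starts its supply rule with "Each in-house foster carer or kinship carer who is caring for a child or young person supported by a social worker".

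The Standard errors section recognises homes with more than one child: "Children are clustered into sibling groups, households (e.g. with other children in foster care". It does not say how many teams such a home may span.

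The Regression specification gives each carer one team c, which carries the treatment variable, the team characteristics and the error cluster. The carer covariates are gender, employer and years of experience, where data can be matched, plus the earlier outcome score. No section says which child's team counts when a carer has children from several teams.

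**The concern.** Teams are randomised, and the carer's arm is derived from them. If any one intervention-team child makes the carer treated, while control status requires that there be none, carers linked to more teams have more chances of entering the treated group. The two groups then differ in expectation on the number of teams, and so on the number of unrelated placements. That characteristic may well go with carer confidence, which is the outcome. The direction is not known: carers with several placements could be more confident or less.

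The model is also incomplete for these carers. A home with children from two teams is not nested in either, so the team covariates and the cluster are undefined.

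**Working it through.** The protocol gives no figure on this point, so there is none to reproduce.

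**Inputs from the protocol**
- Allocation (Sample size / MDES calculations): "treatment assigned at the social worker team level to 50% of the teams".
- Re-randomisation trigger (Randomisation): "the proportion of teams of that type within the local authority assigned to the intervention to be greater than 0.75 or less than 0.25", except where there is only one team of that type.
- Looked-after teams (Table 1): Bexley 3, Haringey 2, Oxfordshire 8 (7 plus the unaccompanied children team), Warwickshire 1.

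**Assumptions (not in the protocol)**
- f, the share of carers with children from two randomised teams: 5% to 40%.
- d, the difference in self-efficacy between multi-team and single-team carers: 0.2 to 0.5 SD.

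**Step 1: chance of being coded treated.** For k independent 1:1 teams it is 1 − 0.5^k: 0.50, 0.75 and 0.875 for k = 1, 2, 3. For two looked-after teams in a stratum of N teams with m treated it is 1 − C(N−m,2)/C(N,2):
- Haringey: N = 2, and the limits force m = 1. The result is 1.00, against 0.50 for one team.
- Bexley: N = 3. With m = 1 it is 0.67 against 0.33; with m = 2 it is 1.00 against 0.67.
- Oxfordshire: N = 8. If m = 4 it is 1 − 6/28 = 0.79, against 0.50.

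**Step 2: make-up of the groups (independent 1:1 teams).** Multi-team share among treated = 0.75f / [0.75f + 0.5(1−f)]. Among control = 0.25f / [0.25f + 0.5(1−f)].

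**Step 3: unadjusted bias** = d × (treated share − control share).

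| f | Treated | Control | Gap | Bias, d = 0.2 | Bias, d = 0.5 |
|---|---|---|---|---|---|
| 5% | 7.3% | 2.6% | 0.048 | 0.010 | 0.024 |
| 20% | 27.3% | 11.1% | 0.162 | 0.032 | 0.081 |
| 40% | 50.0% | 25.0% | 0.250 | 0.050 | 0.125 |

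**Step 4: simulation with no true effect** (4,000 runs, 30 teams with 15 treated, 800 carers, f = 20%, d = 0.3). Coding by any child gives a mean estimate of +0.050 SD. The formula agrees: with 15 of 30 teams treated, the two-team probability is 1 − 105/435 = 0.759, the group shares are 27.5% and 10.8%, and 0.3 × 0.167 = 0.050. Adjusting for multi-team status gives −0.001 SD, and coding by one index child's team gives −0.001 SD.

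**Step 5: does the earlier score repair it?** Research questions and the Survey section place the first carer survey at T6 (October 2021), after the launch on 10 May 2021. A sentence under Previous outcome measures puts the carers' earlier measure at T0 or entry to services, and the Data collection schedule lists T1, but no T0 carer survey is described. A T6 score would still absorb part of a stable difference between carers. As an illustration only, take the scale's test-retest value of 0.73 as the slope, so that 27% of the bias remains. The 5% row becomes 0.003 to 0.006 SD and the 40% row 0.014 to 0.034 SD. If Kitbag has already moved self-efficacy by T6, the same adjustment removes part of the real effect.

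**The case against.** **Another reading is possible.** The wording could mean one particular child. The Covariates section speaks of a carer no longer fostering the child, the Dosage section says carers' outcomes are collected with the child's, and the model gives each carer one team. A separate analysis plan might fix the link. This shows that an index-child structure would suit the model. It does not show that the protocol has one: the stated rule is one such child or else 0, the supply rule matches it, and no index child is named.

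**The numbers are assumed.** This stands. Neither f nor d is in the protocol, and the Standard errors section shows several children per home, not several teams. Warwickshire holds 148 of the 424 intervention-group carers in Table 2 (35%) and has one eligible looked-after team, so a mixed home there needs a second team type. With a small share the bias is small, and the earlier score would shrink it. The survey's assumed 10% response rate may well be the larger problem for this outcome.

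**Stronger readings to avoid.**
- A reader might infer that secondary outcome 5 is not a randomised comparison at all. It is for single-team carers. For multi-team carers the coding is still a function of randomised teams, with unequal but largely known probabilities.
- A reader might infer that the child outcomes are biased too. They are coded by the child's own team. A control-team child living with a carer who holds a Kitbag would be dilution under the stated intention-to-treat rule. The Randomisation section accepts some cross-team contamination ("we believe that this is sufficiently limited that team-level randomisation remains most appropriate"), though it does not discuss this route.
- A reader might infer that the contrast between in-house and other placements claims to isolate the carer's causal contribution. The protocol calls that contrast indicative and non-causal.

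**Conclusion.** The carer coding is wrong as written. The probability of being coded treated depends on how many randomised teams hold the carer's children, and neither the listed covariates nor the T6 score removes that dependence. Carers with several teams also have no defined cluster or team covariates.

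The fault in the rule follows from the text alone. Its numerical effect does not: it runs from negligible to about 0.125 SD unadjusted across the assumed ranges, and less with the earlier score in the model. It touches one secondary survey outcome and leaves the primary outcome alone. It should be corrected because the correction is cheap.

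**What to change.** Under Independent variable of interest: treatment, define each carer's arm, cluster and team covariates by the team of one index child, chosen at carer entry by a rule that ignores arm (for example, the eligible child placed longest). Repeat the carer analysis excluding carers with children from more than one randomised team.

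The cost is a sentence or two and a carer or placement identifier in the local authority extract. The downside is that some carers coded control will hold a Kitbag through another child. With independent 1:1 teams these are 0.25f / 0.5 = f/2 of the control group: 2.5% at a 5% share and 20% at 40%. If the effect is the same for all carers, the estimate shrinks by that fraction. This is slight when few carers have several teams, and the repeat analysis shows whether it matters.

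If the any-child coding is kept, adjust for the number of teams within local authority and team-type stratum, since Step 1 shows that the number of teams alone does not fix the probability. Exclude carers whose probability of treatment is 0 or 1, such as those with both Haringey looked-after teams, because adjustment cannot help there. A rule is still needed for those carers' cluster and team covariates.

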Local authority	Number of social workers and family support workers in teams in the intervention group	Hold back for staff turnover (assume 15%)	Number of foster carers (including kinship carers) in the intervention group	Hold back for new foster carers (assume 10%)	Number of Kitbags for social workers in the fostering service	Total
Bexley	33	5	57	6	2	103
Haringey	28	4	100	10	2	144
Oxfordshire	120	18	119	12	4	273
Warwickshire	119	18	148	15	10	310
Total	300	45	424	43	18	830

Children and young people

Children and young people aged 4-18 years old who have an open case in May 2021 or whose case opens between May 2021 and December 2021 and supported by social workers and family support workers in eligible teams are eligible for the programme. Only those whose

case starts before December 2021 will be eligible to allow for the minimum number of sessions to feasibly be delivered with a Kitbag before the evaluation period concludes (May 2022).

The number of children and young people who are classified as children in need (according to the Department for Education’s broad definition including children on a child in need plan, child protection plan and children in care) across these four local authorities is approximately 13,000. We estimate that there are approximately 9300 eligible children and young people across the four local authorities (henceforth we refer to them as the population).⁶

Table 3: Number of children in need in Bexley, Haringey, Oxfordshire and Warwickshire between 2019 and 2020

Local authority	Number of children in need at 31 March (2019)	Number of children in need at 31 March (2020)
Bexley	1594	1757
Haringey	2073	2284
Oxfordshire	4511	4750
Warwickshire	3914	4073
Total	12092	12864

Recruitment

Social workers / family support workers

Social workers will be identified from their membership in eligible teams, as per the HR IT systems of the local authorities. The social workers and family support workers will be asked to provide their informed consent before participating in the primary data collection (survey, interviews). They will also be notified of the use of their absence data in the email inviting them to participate in the survey at T6 (prior to the data sharing) and of their rights in relation to the processing.

Children and young people

Children and young people will be identified as eligible by their allocation to a social worker in an eligible team.

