Pseudonymised administrative data on interactions with children's social care (CIN plans, CPP, CLA and case closure) will be requested from local authorities. Consent for the sharing of this data will not be explicitly sought from families. This is because we consider the risk to participants arising from the sharing and processing of this data for the purpose of the evaluation to be very low, and the benefit to accessing the data for all eligible participants to be high. The risk that the eligible participants are identified is very low, and the risk of a data breach will be carefully managed so that it remains low. The benefit of accessing the data for all eligible participants is that we maintain statistical power and reduce the risk of selection bias into the sample, allowing for better - unbiased and more precise - estimates of the treatment effect, making the evaluation much more useful to decision-makers. Having said this, participants will be able to withdraw their consent for their data to be processed for the evaluation if they so choose to via a form on the WWCS website. Please see the Data Protection section below for more details on the data governance of this.

Social workers and family support workers

Pseudonymised administrative data on the sickness absence of social workers and family support workers will be requested from local authorities. Consent for the sharing of this data will not be explicitly sought from social workers for the same reasoning as above.

Summary statistics about access to Kitbag Online will be requested from IFF. Given that the social worker participants will not have accessed the website before, it may be possible to add consent to share for purposes of the evaluation into the terms of use. We are currently investigating this with the delivery partners.

Implementation and process evaluation

Focus group discussions and interviews

Focus group discussion and Interview participants will be sent an information sheet in advance of the interview. Before the interview commences, the researcher will ask the participant if they have read and understood the information sheet, and whether they have any questions. The researcher will then elicit consent for participation and for the interview to be recorded. When eliciting consent for participation in interviews, researchers will make clear the limits of confidentiality (See Section D for further information).

Observation

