January 2021	Advisory Board meetings	UoS/IFF
January - March 2021	Site selection, engagement, set up meeting and work	All
March 2021	Ethics approval obtained	WWCS
March 2021	Randomisation of teams to kitbag	WWCS
April 2021	Kitbag leads identified and appointed	LA partners
Before data collection	Trial protocol drafted and published	WWCS
May 2021	Kitbag distribution	UoS/IFF

10th May 2021	Launch of project in 4 sites as one online event	UoS/IFF + LA partners
May 2021 - April 2022	Regular Kitbag use	LA partners
May 2022	Endline data collection	LA partners / WWCS
June - July 2022	Final analysis and report	WWCS

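### Children whose cases open after the March 2021 team randomisation take the arm of the team that receives them, and no planned analysis isolates the children already held at randomisation

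*Protocol*

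**What the plan says.** **Timing.** The Timeline lists "Randomisation of teams to kitbag" under March 2021, appointment of Kitbag leads under April and Kitbag distribution under May. A footnote to Randomisation adds that, because data were delayed, "the teams from Oxfordshire County Council were allocated separately". No date is given for that step. Oxfordshire supplies 30 of the 60 teams in Table 1.

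**Who is in the sample.** Under Participants (Children and young people), eligible children are those aged 4–18 who "have an open case in May 2021 or whose case opens between May 2021 and December 2021". The next sentence closes entry before December, which is one month shorter.

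**How a child gets an arm.** Under Independent variable of interest, children enter either at randomisation or when they become eligible, and "they will be allocated to treatment if the team of their allocated social worker was randomised to treatment". Handling non-compliance repeats this: the arm is that of the team supporting the child "at the point they entered the sample (either at randomisation or when their case started), irrespective of their use of Kitbag".

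**Visibility.** The intervention description places two Designated Kitbag Leads in each intervention team and none in control teams. No masking of allocation from those who place cases is described.

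**Routing and selection.** The only remark on how cases reach teams is in Sample size / MDES calculations, where the ICC of 0.03 is justified by saying that cases are not grouped by likeness beyond level of involvement. Consent procedures says that using administrative data for all eligible children will "reduce the risk of selection bias into the sample".

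**The concern.** For children held by a team when it was randomised, the arm is a product of randomisation. For children whose case opens later, it is a product of a placement decision made once the arms could be known. Intention to treat fixes the arm from entry onward and so cannot protect the step at which the arm is acquired. The administrative-data argument deals with consent, not with which team receives a case.

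If new cases thought likely to benefit, or likely to close, went preferentially to one arm's teams, expected status change would differ between arms before any Kitbag use. The primary outcome is the sum of status changes, so the difference would enter the treatment coefficient. Team-clustered standard errors do not remove it, and the child covariates remove only what they record.

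No planned analysis isolates the children already held at randomisation. The dosage analysis does not do so: it splits treated children by months of exposure, mixes early leavers with late entrants, and pools all controls.

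**Working it through.** **1. The plan's own figure.** Inputs from the MDES table: 60 teams, half treated; 150 children per team; ICC 0.03; child R² 0.8; team R² 0.1 with 3 covariates; two-sided 5%; power 80%. For the blocked cluster design, with 4 authorities and df = 60 − 2×4 − 3 = 49:

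MDES = (t₀.₉₇₅ + t₀.₈₀) × √[0.03×0.9/(0.25×60) + 0.97×0.2/(0.25×60×150)] = 2.859 × √(0.001800 + 0.000086) = 2.859 × 0.0434 = 0.124.

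The stated value is 0.127. Power at 0.127 is 0.818, so the figure is reproduced closely enough to serve as a yardstick.

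**2. Share of late entrants.** The protocol does not give it. The Dosage section expects 50% of children present at T0 (April 2021) to have left by T13 (May 2022). Assume that inflow equals outflow. Inflow relative to the starting caseload is then 0.5×m/T (linear) or ln 2×m/T (constant hazard) for an m-month window over T months, and share = inflow/(1 + inflow).

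| Window | T | Linear | Constant hazard |
|---|---|---|---|
| 7 months (before December) | 13 | 0.269/1.269 = 21% | 0.373/1.373 = 27% |
| 8 months (May–December) | 13 | 0.308/1.308 = 24% | 0.427/1.427 = 30% |
| 8 months | 12 | 0.333/1.333 = 25% | 0.462/1.462 = 32% |
| 10 months (adding March–May) | 13 | 0.385/1.385 = 28% | 0.533/1.533 = 35% |

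The range is roughly 21–35%. It is the share entering late, which is an upper limit on the share whose arm anyone could influence.

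**3. Illustrative bias.** The protocol gives no steering rate, so these rates are assumptions. Suppose a fraction s of control-bound new cases, with expected outcome d SD from average, goes to intervention teams instead. The gap between arms among late entrants is s·d/(1+s) + s·d/(1−s). Multiply by the late share (24–30% here) and compare with SE = 0.127/2.8 = 0.0454.

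- s = 5%, d = 0.3: gap 0.0143 + 0.0158 = 0.030; whole-sample shift 0.007–0.009 SD; the 5% test runs at 5.3–5.5%.
- s = 10%, d = 0.5: gap 0.0455 + 0.0556 = 0.101; shift 0.024–0.030 SD, or 19–24% of 0.127; the 5% test runs at 8–10%.

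Across the full 21–35% share the shifts are 0.006–0.011 and 0.021–0.035 SD. All of these precede covariate adjustment. If the covariates explained 80% of the steered difference, the second case would fall to 0.2 × 0.024–0.030 = 0.005–0.006 SD and the test would run at about 5.1–5.2%. The protocol supports 0.8 for the SDQ only, not for the current primary outcome.

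**4. Cost of a closed cohort.** Replace 150 by 150×(1 − share) in step 1.

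- Child R² 0.8: 0.124 becomes 0.125, about 1% larger.
- Child R² 0, share 24–30%: 0.135 becomes 0.139–0.141, 3–4% larger. At a share of 35% it is 0.142, 5% larger.

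Precision depends mainly on the 60 teams.

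**5. Two definitions of the open-case group.** Participants sets it in May 2021; the treatment definition and Handling non-compliance set it at randomisation. A case opened in April 2021, or moved between teams between March and May, can take a different arm depending on which text is followed. No assumption about steering is needed for this.

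**The case against.** A reader might infer that a quarter or more of the primary sample is exposed to selection. The documents do not support that. Table 1 names many teams by area (Bexley's family support teams, Warwickshire's safeguarding teams, Oxfordshire's disability teams). Others look specialist or are alone in their stratum, such as No Recourse to Public Funds, Unaccompanied Children and the one Warwickshire CLA team. There a new case may have only one possible destination. The remark on the ICC, though not written as a safeguard, points away from routing by child characteristics, and level of involvement is a covariate. No passage says who places cases or what they know about the arms. Steering in opposite directions in different authorities would partly cancel. All of this stands, and it limits the size of the problem.

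A reader might also infer that the primary population must be replaced. That does not follow either. The protocol deliberately includes new cases. A cohort fixed at March alone would add children whose cases close before Kitbags are distributed: over two months, 0.5×2/13 = 8% (linear) to 1 − 2^(−2/13) = 10% (constant hazard).

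The Missing data section does plan a baseline table by arm that includes joiners. It is organised by survey response and yields no separate effect estimate, so it helps only in part.

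What the objection does not remove is the sequence itself. Several same-type teams differ only by number (Oxfordshire Family Solutions Plus North 1–6, Haringey Safeguarding and Support 1–6), so a choice between arms may exist. The population and arm rules are fixed in this protocol rather than deferred.

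**Conclusion.** The structural point holds. Late entrants acquire their arm after a visible allocation, and the protocol describes neither concealment nor a routing rule. They make up about 21–35% of the sample if inflow matches the stated 50% turnover; the steerable part is smaller and cannot be derived from the documents. The bias figures, from under 0.01 SD to about 0.03 SD at a 24–30% share, rest wholly on assumed steering rates. The documents contain no evidence that steering occurs. For Oxfordshire the interval between randomisation and entry is not established. This is a cheap improvement that lets readers separate a Kitbag effect from case routing, not a flaw that invalidates the primary analysis.

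**What to change.** Keep the pooled population as primary and add the following to the Analysis plan:

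1. **Key sensitivity analysis.** A closed cohort of children aged 4–18 held by an eligible team on the date that authority's teams were randomised (Oxfordshire's own date to be stated) and still open in May 2021 when Kitbags are distributed. The arm is fixed by the team on the randomisation date. The May condition falls after randomisation but before distribution, so Kitbag use cannot have affected it; report by arm how many children it removes.
2. **Checks on later entrants.** New cases per team and entry characteristics, by arm and stratum, and a test of treatment × late entry.
3. **Interpretation rule.** A pooled effect that the closed cohort does not support will not be read as randomised evidence.
4. **Reconciliation.** Make Participants, the treatment definition and Handling non-compliance use one date for the open-case group, and settle whether entry runs through December or stops before it.

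The cost is protocol wording, date filters on administrative data already being requested, and a little extra analysis. The closed-cohort estimate is slightly less precise, by the amounts in step 4 of the working. The primary estimate loses nothing.
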